## **4.4. Duration of Treatment and Subject Participation**

**Screening:** Up to 28 days.

**Baseline:** 7 days before first dose of INCB050465

**Treatment:** Begins with the first dose of INCB050465 (Day 1). Treatment will continue as long as the regimen is tolerated and the subject does not meet discontinuation criteria. Subjects will receive daily doses of INCB050465 throughout the study, or daily doses for 8 weeks, followed by once-weekly administration or QD administration (determined by the study part to which subjects were enrolled). Subjects who discontinue study treatment will be followed for subsequent MF treatments and survival.

**Follow-up:** 30 to 35 days after the last dose of medication is taken.

**Survival follow-up:** Until subject dies.

It is estimated that an individual subject will participate for approximately 24 months.

## **4.5. Overall Study Duration**

The study begins when the first subject signs the ICF. The end of the study will occur when all subjects have completed the follow-up visit or discontinued study.

## **4.6. Study Termination**

The investigator retains the right to terminate study participation at any time, according to the terms specified in the study contract. The investigator is to notify the institutional review board (IRB)/independent ethics committee (IEC) in writing of the study's completion or early termination, send a copy of the notification to the sponsor or sponsor's designee, and retain 1 copy for the site study regulatory file.

The sponsor may terminate the study electively, or if required by regulatory decision. If the study is terminated prematurely, the sponsor will notify the investigators, the IRBs and IECs, and regulatory bodies of the decision and reason for termination of the study.

## 5. TREATMENT

### 5.1. Treatment Assignment

#### 5.1.1. Subject Numbering and Treatment Assignment

Each subject will be identified in the study by a unique subject ID number, which is a combination of the site ID and subject number. Site staff will work through the interactive web response system (IRT/IWRS) to obtain subject number.

Enrollment for Part 1 will be controlled by distribution of enrollment slots to the clinical sites by the sponsor or its designee.

Enrollment for Part 2, Part 3, and Part 4 will be controlled by the IRT/IWRS.

Subjects who are screen failures and are not enrolled in the study will still have data entered into the case report form (CRF). Consult the CRF instructions to determine which CRF pages must be completed for screen failures.

#### 5.1.2. Randomization

For Part 2, Part 3, and Part 4, randomization will occur centrally by IRT/IWRS. Full details will be provided in the INCB 50465-201 Study Manual.

## 5.2. Cohorts and Treatment Groups

### 5.2.1. Part 1: Safety Run-In Portion

Up to 3 doses of INCB050465 were to be explored in successive cohorts (see [Table 4](#)). All subjects would also receive the same ruxolitinib dose regimen that individual subjects were taking at the time of the screening visit.

**Table 4: Part 1 Treatment Groups**

Cohort	Dose Regimen
Cohort 1	INCB050465 10 mg QD for 8 weeks followed by once-weekly dosing at 10 mg.
Cohort 2	INCB050465 20 mg QD for 8 weeks followed by once-weekly dosing at 20 mg
Cohort 3	INCB050465 5 mg QD for 8 weeks followed by once-weekly dosing at 5 mg

After the 28-day safety evaluation period, safety run-in subjects may receive additional combination therapy of INCB050465 plus ruxolitinib long as adequately tolerated and if no

discontinuation criteria are met. Cohorts 1 and 2 were completed. No DLTs were observed. Part 1 is complete.

### **5.2.2. Part 2, Part 3, and Part 4 Treatment Groups: Randomized Portion**

TG10: Ruxolitinib at stable dose plus INCB050465 at 10 mg QD for 8 weeks followed by 10 mg once weekly.

TG20: Ruxolitinib at stable dose plus INCB050465 at 20 mg QD for 8 weeks followed by 20 mg once weekly. Note that enrollment in Part 2 was suspended with implementation of Amendment 5.

TG5: Ruxolitinib at stable dose plus INCB050465 at 20 mg QD for 8 weeks followed by 5 mg QD. Note that enrollment in Part 3 will be suspended with implementation of Amendment 6.

TG5I/M: Ruxolitinib at stable dose plus INCB050465 at 20 mg QD for 8 weeks followed by 5 mg QD. Note this Part 4 dose group is identical to TG5 group in Part 3.

TG5D: Ruxolitinib at stable dose plus INCB050465 at 5 mg QD.

### **5.2.3. Crossover of Part 2 or Part 3 Subjects**

It is anticipated that approximately 15 to 20 subjects will have been enrolled into Part 2. With IRB approval of Protocol Amendment 5 at a given site, subjects randomized to TG10 at that site may cross over to either 20 mg QD followed by 5 mg QD after Week 8 (if subject is within the first 8 weeks of treatment at the time of crossover), or to 5 mg QD (if subject is beyond 8 weeks of treatment and receiving 10 mg once weekly at the time of crossover). With IRB approval of Protocol Amendment 6 at a given site, subjects randomized to TG20 at that site may cross over to 5 mg QD once Week 8 has been reached. All potential crossover subjects must meet all of the following criteria:

1. Spleen size by palpation at most recent visit has decreased by < 25% from baseline while on study.
2. Has recent history of adequate bone marrow reserve as demonstrated by the following:
  - a. Platelet count  $\geq 50 \times 10^9/L$  in the 4 weeks before crossover.
  - b. ANC levels  $\geq 0.5 \times 10^9/L$  in the 4 weeks before crossover.
3. Has adequate liver function at most recent study visit as demonstrated by the following:
  - a. Direct bilirubin  $< 2.0 \times$  the ULN. (NOTE: direct bilirubin will only be determined if total bilirubin is  $\geq 2.0 \times$  ULN).
  - b. ALT or AST  $< 2.5 \times$  ULN.
4. Has adequate renal function at most recent visit as demonstrated by creatinine clearance  $> 50 \text{ mL/min}$  measured or calculated by Cockcroft-Gault equation.
5. Subject has been at least 85% compliant with study drug administration per drug accountability assessments at visits to date.
6. Subject has not developed a cardiovascular or gastrointestinal condition since Day 1 that would have excluded him/her from study entry.

Subjects who do not meet these criteria, or subjects who do meet the criteria but do not wish to cross over, may continue on the originally assigned regimen, and may crossover at any time provided the criteria for crossover are met and crossover is determined by subject and investigator to represent the best option.

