### **3.3. Subject Exclusion Criteria**

A subject who meets any of the following criteria will be excluded from the study:

1. Use of experimental drug therapy for MF or any other standard drug (eg, danazol, hydroxyurea, etc.), with the exception of ruxolitinib within 6 months of starting study (combination) therapy and/or lack of recovery from all toxicities from previous therapy (except ruxolitinib) to Grade 1 or better.
2. Inability to swallow food or any condition of the upper gastrointestinal tract that precludes administration of oral medications.
3. Unwillingness to be transfused with blood components.
4. Recent history of inadequate bone marrow reserve as demonstrated by the following:
  - a. Platelet count  $< 50 \times 10^9/\text{L}$  in the 4 weeks before screening or platelet transfusion(s) within 8 weeks before screening.
  - b. Absolute neutrophil count (ANC) levels  $< 0.5 \times 10^9/\text{L}$  in the 4 weeks before screening.
  - c. Subjects with peripheral blood blast count of  $> 10\%$  at the screening or baseline hematology assessments.
  - d. Subjects who are not willing to receive RBC transfusions to treat low hemoglobin levels.
5. Inadequate liver function at screening visit as demonstrated by the following:
  - a. Direct bilirubin  $\geq 2.0 \times$  the upper limit of laboratory normal (ULN). (NOTE: direct bilirubin will only be determined if total bilirubin is  $\geq 2.0 \times$  ULN).
  - b. ALT or AST  $> 2.5 \times$  ULN.
6. Inadequate renal function at screening visit as demonstrated by creatinine clearance  $< 50 \text{ mL/min}$  measured or calculated by Cockcroft-Gault equation, or glomerular filtration rate  $< 50 \text{ mL/min}/1.73 \text{ m}^2$  as calculated using the Modification of Diet in Renal Disease formula.
7. Active bacterial, fungal, parasitic, or viral infection that requires therapy. Subjects with acute infections requiring treatment should delay screening/enrollment until the course of therapy has been completed and the event is considered resolved. Prophylactic antibiotics will be permitted.
8. Active hepatitis B virus (HBV) or hepatitis C virus (HCV) infection that requires treatment or at risk for HBV reactivation. Hepatitis B virus DNA and HCV RNA must be undetectable upon testing. At risk for HBV reactivation is defined as hepatitis B surface antigen positive or anti-hepatitis B core antibody positive. Cytomegalovirus must be undetectable by polymerase chain reaction.

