## **4.3. Number of Subjects**

### **4.3.1. Planned Number of Subjects**

Part 1 was expected to enroll 9 to 18 subjects (10 were enrolled), Part 2 was planned to enroll a total of 60 subjects before termination; because Part 3 was added, only 20 subjects were enrolled. Part 3 was expected to enroll approximately 52 subjects; approximately 5 subjects may be enrolled. Part 4 will enroll approximately 55 subjects. Twenty or more clinical sites will participate.

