**Table 5: Guidelines for Interruption and Restarting of INCB050465**

ADVERSE EVENT	ACTION TAKEN
Chemistry	

AST and/or ALT are <math>> 5.0 \times</math> ULN.

 
Note: In subjects with bone metastasis-related elevations at baseline, contact sponsor to discuss clinical management and possible dose reductions.
	
Step 1: Interrupt study drug up to 2 weeks (14 days) until the toxicity has resolved to <math>\leq</math> Grade 1 except by approval of the medical monitor.
 
Step 2: Restart study drug at same dose. If assessed as related to study drug, restart study drug at next lower dose (or at 25% reduction, rounded down to the nearest pill strength); monitor as clinically indicated.

Hematology	

ANC <math>\leq 1.0 \times 10^9/L</math> unless because of underlying disease. Applies only if this represents a worsening grade from baseline.

Platelet count <math>\geq 50 \times 10^9/L</math> and <math>< 75 \times 10^9/L</math> unless because of underlying disease. Applies only if this represents a worsening grade from baseline.

	
Step 1: Interrupt study drug up to 2 weeks (14 days) until the toxicity has resolved to <math>\leq</math> Grade 1 or pretherapy baseline.
 
Step 2: Restart study drug at same dose and monitor as clinically indicated.

Grade 4 ANC (<math>< 0.5 \times 10^9/L</math>) regardless of baseline grade.

<math>\geq</math> Grade 3 ANC with an oral temperature of at least <math>38.5^\circ C</math> OR with <math>\geq</math> Grade 3 infection regardless of baseline grade.

Platelet count is <math>< 50 \times 10^9/L</math>, regardless of baseline grade.

	
Step 1: Interrupt study drug up to 2 weeks (14 days) until the toxicity has resolved to <math>\leq</math> Grade 1 or pretherapy baseline.
 
Step 2: Restart study drug at same dose. If assessed as related to study drug, restart study drug at next lower dose; monitor as clinically indicated.

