3.5. Crossover Portion

With IRB approval of Protocol Amendment 5 at a given site, participants randomized to TG10 in Part 2 at that site may cross over to either 20 mg QD followed by 5 mg QD after Week 8 (if participant is within the first 8 weeks of treatment at the time of crossover), or to 5 mg QD (if participant is beyond 8 weeks of treatment and receiving 10 mg once weekly at the time of crossover). With IRB approval of Protocol Amendment 6 at a given site, participants randomized to TG20 at that site may cross over to 5 mg QD once Week 8 has been reached. All potential crossover participants must meet the criteria listed in Protocol Amendment 6, Section 5.2.3.

Participants who do not meet these criteria, or participants who do meet the criteria but do not wish to cross over, may continue on the originally assigned regimen, and may crossover at any time provided the criteria for crossover are met and crossover is determined by participant and investigator to represent the best option.

The crossover portion starts when the participants are assigned to and receive their first dose of a different treatment. The original portion of the study for crossover participants ends the day before crossover.

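### Crossover criterion 3b is satisfied when just one of ALT and AST is below 2.5 × ULN, so a subject whom the entry criteria would exclude on liver function can cross over

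*Protocol*

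**What the plan says.** Protocol Section 5.2.3 sets the conditions for moving to a different INCB050465 regimen. It opens with "All potential crossover subjects must meet all of the following criteria". Criterion 3 begins "Has adequate liver function at most recent study visit as demonstrated by the following" and has two parts: 3a on direct bilirubin, and 3b, "ALT or AST $< 2.5 \times$ ULN".

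The matching entry rule is exclusion 5b in Section 3.3: "ALT or AST $> 2.5 \times$ ULN".

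SAP Section 3.5 adds no threshold of its own and refers back to the protocol: "All potential crossover participants must meet the criteria listed in Protocol Amendment 6, Section 5.2.3".

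Once a subject is on treatment, the transaminase row of Table 5 (Section 5.5.6) applies when "AST and/or ALT are > 5.0 \times ULN". Section 5.5.6 describes the rules in that table as guidelines.

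**The concern.** The same connective is used in an exclusion and in a requirement, where it has opposite effects. In the exclusion, "ALT or AST $> 2.5 \times$ ULN" removes anyone with at least one raised enzyme. In the requirement, "ALT or AST $< 2.5 \times$ ULN" admits anyone with at least one enzyme below the limit. Turning an exclusion of the form A-or-B into a requirement gives not-A **and** not-B. Item 3b reverses the inequality but keeps the original connective.

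Two things are at stake. First, the criterion is applied at the moment the subject's nominal weekly dose goes up, with a drug class for which Section 1.8.4 names hepatotoxicity as a risk. Second, one site may apply 3b literally and another may read it as mirroring the entry rule, and both would believe they were complying.

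**Working it through.** No sample size, power or alpha is involved, so this is a check of logic plus simple dose arithmetic.

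**1. The rules side by side** (enzymes in multiples of ULN)

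- Entry, Section 3.3 item 5b: passes if max(ALT, AST) ≤ 2.5.
- Crossover, Section 5.2.3 item 3b as written: passes if min(ALT, AST) < 2.5.
- Interruption, Table 5: triggered if max(ALT, AST) > 5.0.

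| ALT | AST | Entry 5b | Crossover 3b as written | Table 5 interruption |
|---|---|---|---|---|
| 2.0 | 2.0 | pass | pass | no |
| 4.5 | 2.0 | **fail** | **pass** | **no** |
| 1.0 | 4.0 | **fail** | **pass** | **no** |
| 4.5 | 4.5 | fail | fail | no |

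The gap is every pair with one enzyme below 2.5 and the other above it. Taking each enzyme at 1.0, 2.4, 2.5, 2.6, 3.0, 4.0, 5.0 and 5.1:

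- Pairs that pass 3b but fail entry: 2 low values × 5 high values × 2 orderings = 20.
- Of these, pairs that do not trigger Table 5: 2 × 4 × 2 = 16.
- Pairs in the gap if both enzymes must be below 2.5: 0.

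Requiring both to be ≤ 2.5 also leaves none, because that is exactly the entry condition.

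**2. Does another provision close the gap?**

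- Item 3a covers direct bilirubin only.
- Criterion 6 brings back entry exclusions for cardiovascular and gastrointestinal conditions, but not hepatic ones.
- The synopsis and Section 4.1.3 require that hepatic disease not be uncontrolled. They give no transaminase limit and refer onward to the crossover list.
- SAP Section 3.5 only points back to Section 5.2.3.
- Table 5 starts above 5.0 × ULN.

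None restores a both-below condition.

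**3. Is it a deliberate relaxation?** The neighbouring thresholds in Section 5.2.3 are the Section 3.3 exclusions turned round: platelets < 50 becomes ≥ 50, ANC < 0.5 becomes ≥ 0.5, direct bilirubin ≥ 2.0 × ULN becomes < 2.0 × ULN, and creatinine clearance < 50 becomes > 50. Only 3b joins two analytes, and only there does the conversion fail. No text argues for a looser liver standard at crossover. That points to a slip, though the documents do not give the drafting history.

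**4. Dose change at crossover** (regimens from Sections 5.2.2 and 5.2.3)

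| Subject | Current weekly dose | Weekly dose after crossover | Ratio | Weekly dose in first 8 weeks |
|---|---|---|---|---|
| TG10, after Week 8 | 10 mg | 5 × 7 = 35 mg | 3.5 | 10 × 7 = 70 mg |
| TG20, after Week 8 | 20 mg | 5 × 7 = 35 mg | 1.75 | 20 × 7 = 140 mg |
| TG10, within Week 8 | 10 × 7 = 70 mg | 20 × 7 = 140 mg | 2.0 | 70 mg (current) |

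**5. How many subjects?** For Part 2, Section 4.3.1 says "only 20 subjects were enrolled"; for Part 3 it expects approximately 5. That gives 20 + 5 = 25. Only the TG20 subjects in Part 3 can cross over, so with a 3:2 split about 2 of the 5 would count, giving about 22. The Part 3 figure is itself approximate.

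**6. Can the two enzymes diverge?** Section 1.6.1.2 reports raised ALT in 27.2% and raised AST in 18.6% of subjects in the pivotal ruxolitinib studies. If both percentages share a denominator, at least 27.2 − 18.6 = 8.6% had raised ALT without raised AST. The degree of elevation is not given, so this shows divergence but does not estimate how many would fall in the gap.

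**The case against.** The literal reading is hard to dispute; the real argument is about how much it matters.

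- **The protocol already tolerates this band on treatment.** Table 5 does not call for interruption until an enzyme exceeds 5.0 × ULN, so a subject on 20 mg daily may stay on it with ALT at 4.5 × ULN. Entry and on-treatment limits differ by design, and failing the entry limit is not in itself evidence of harm. This stands. It does not explain why a crossover criterion with its own 2.5 × ULN limit should apply that limit to only one enzyme.
- **The dose ratios need context.** After Week 8, crossover to 35 mg a week is half of what a TG10 subject received in the first 8 weeks and a quarter of what a TG20 subject received. The single dose also falls, from 10 or 20 mg to 5 mg. This stands and limits the consequence.
- **The only route above earlier exposure is probably closed.** Moving from 70 to 140 mg a week needs a TG10 subject still within Week 8. Part 2 enrollment ended site by site with approval of Amendment 5 (23 March 2018), and Amendment 6 (11 October 2018) treats it as finished. This is likely right.
- **The liver signal for this compound is mild.** Section 1.8.4 bases the class risk on idelalisib, and reports preclinical hepatotoxicity with INCB050465 only at more than 65-fold the projected exposure at 10 mg daily. Section 1.8.6 expects no added hepatic risk from the combination and provides for regular liver tests. This stands.
- **Judgement offers some cover.** Section 5.2.3 leaves later crossover to the subject and investigator, and many sites would probably read 3b as the entry rule. That is partial protection, not a limit.
- **Enrollment ended early**, as SAP Section 10.2.3 records. However, Section 5.2.3 lets eligible subjects cross over at any time, so the end of enrollment does not by itself make the criterion moot.

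**Conclusion.** The concern holds. As written, 3b admits subjects with one transaminase above 2.5 × ULN whom the entry rule would exclude, and between about 2.5 and 5 × ULN no other numerical rule stops the crossover.

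The consequence is small and concerns patient safety. The pool is roughly 22 to 25 subjects on the planned numbers, the number with a single raised enzyme is unknown, and the post-Week-8 weekly doses stay below those of the first 8 weeks. The primary comparison of TG5D with TG5I/M + TG5, its power and its alpha are unaffected: subjects in those groups do not cross over, and SAP Sections 5.2 and 5.3.1 summarize post-crossover data separately.

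The conclusion rests on reading 3b literally. If every site read it as the entry rule, no subject would be affected, but the text does not ensure that. It is a minor point, worth correcting because the criterion controls eligibility on a safety measure.

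**What to change.** Reword criterion 3b in Protocol Section 5.2.3 to require that ALT and AST are both ≤ 2.5 × ULN. This matches exclusion 5b exactly, including at 2.5 × ULN itself, which entry allows but the present strict inequality does not. The smallest alternative is to keep the strict inequality and change the connective to *and*; this also removes every gap case.

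The cost is a wording change to one line. SAP Section 3.5 refers to the protocol list; if the correction comes in a later amendment, update the amendment number cited there. No analysis, sample size or data collection changes.

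If the protocol is no longer being amended, a note to sites would serve for any subject who may still cross over. For those who already have, ALT and AST at the last visit before crossover can be checked from data already collected.

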### **5.3. Study Drugs**

#### **5.3.1. INCB050465**

##### **5.3.1.1. Description and Administration**

Compound name	INCB050465												
Dosage strengths	1 mg, 2.5 mg, 5 mg, and 20 mg												
Form	Tablet												
Active compound	INCB050465												
Route of administration	Oral												
Dose and regimen for Part 3	20 mg QD for 8 weeks followed by randomization to either 5 mg QD or 20 mg once weekly												
Dose and regimen for Part 4	TG5I/M: 20 mg QD for 8 weeks followed by 5 mg QD until EOT TG5D: 5 mg QD from Day 1 until EOT												
Instructions	
INCB050465 will be taken orally with water in a fasted state except on mornings of monthly study visits (see Table 9) where they must arrive for their study visit in the fasted state for study drug administration at the visit. Subjects should refrain from food consumption for at least 1 hour after administration of INCB050465.
 
For Part 3 subjects only: Once 8 weeks of daily dosing have been completed, subject will switch to either 5 mg QD or 20 mg once weekly, beginning the next weekday after the last daily dose:
 

Last daily dose	First weekly dose	

Monday	Tuesday, then every Tuesday	

Tuesday	Wednesday, then every Wednesday	

Wednesday	Thursday, then every Thursday	

Thursday	Friday, then every Friday	

Friday	Friday (the following week, then every subsequent Friday)	

	Last daily dose	First weekly dose	Monday	Tuesday, then every Tuesday	Tuesday	Wednesday, then every Wednesday	Wednesday	Thursday, then every Thursday	Thursday	Friday, then every Friday	Friday	Friday (the following week, then every subsequent Friday)
Last daily dose	First weekly dose												
Monday	Tuesday, then every Tuesday												
Tuesday	Wednesday, then every Wednesday												
Wednesday	Thursday, then every Thursday												
Thursday	Friday, then every Friday												
Friday	Friday (the following week, then every subsequent Friday)												

Note that subjects must be instructed to withhold the morning dose of INCB050465 and to arrive in the fasted state until reaching the clinic for each study visit where administration will occur (first 24 weeks of therapy only). The dose must be reduced or interrupted for declining platelet count or ANC as described in Section [5.5](#) and will be increased or restarted with recovery of hematologic parameters.

##### **5.3.1.2. Supply, Packaging, and Labeling**

INCB050465 tablets are packaged in high-density polyethylene bottles, no preparation is required.

All Incyte investigational product labels will be in the local language and will comply with the legal requirements of each country and will state "Caution: New Drug--Limited by Federal (or United States) law to investigational use."

